11.2. Second stage analysis – 12 month short-term follow-up (STFU12)

11.2.1. Demographics and Other Baseline Characteristics

Not applicable for this stage of analysis since all information on demographics and other baseline characteristics was already analyzed in the first stage analysis (see 11.1.1).

11.2.2. Primary Efficacy variable

Not applicable for this stage of analysis since all information on the primary efficacy variable was already analyzed in the first stage analysis (see 11.1.2).

11.2.3. Secondary Efficacy variables

Not applicable for this stage of analysis since all information on the secondary efficacy variables was already analyzed in the first stage analysis (see 11.1.3).

11.2.4. Safety variables

11.2.4.1. Safety Endpoint: Time to wound closure

Not applicable for this stage of analysis since all information on this endpoint was already analyzed in the first stage analysis (see 11.1.4.1).

11.2.4.2. Safety Endpoint: Cosmesis and function at 12 months from wound closure

The MVSS score for a patient will be calculated as described in Section 10.3.4.2. The mean and standard error of this MVSS score (for the target wounds) at 12 months will be estimated for each treatment group and presented as shown in Table 4. The treatment groups will be compared using a linear model with MVSS score as the dependent variable. The explanatory variables in the model will include treatment, and the following variables: overall TW depth (all TWs full thickness, mixed TWs, all TWs deep partial thickness), “Total %TBSA per patient” and number of TWs (1, 2, ≥ 3). The coefficient corresponding to the treatment group will be estimated and will represent the estimated mean difference in MVSS score between NexoBrid and SOC adjusted for any imbalance in the stratification factors. The results of the regression analysis will be presented as in Table 7.

A clinically meaningful difference will be incorporated into the analysis that will represent a 1.9 or more units advantage to the SOC group, so that the analysis will show whether the NexoBrid group is estimated to have on average a MVSS score that is not worse by more than 1.9 units than the score for the SOC group. That is, the following hypothesis are about to be tested:

$$H_0: \Delta \geq 1.9 \quad vs. \quad H_1: \Delta < 1.9$$

Where Δ is the mean difference in MVSS score between NexoBrid and SOC adjusted for any imbalance in the stratification factors. These hypotheses will be tested by comparing the 95% confidence interval for the coefficient of the treatment group from the linear model outlined above to the clinically meaningful difference 1.9. The null hypothesis will be rejected if the upper bound of this interval is smaller than 1.9.

For handling of missing data see Section 10.1.2.2.

11.2.4.3. *Safety Endpoint: Cosmesis and function at 24 months from wound closure*

Not applicable for this stage of analysis since the relevant information for all patients is not available yet. This endpoint will be analyzed in the third stage analysis (see 11.3.4.3).

11.2.4.4. *Adverse Events*

In this analysis, only the adverse events occurring after the 3 months follow up and until the 12 months follow up (including AEs from the first stage that are still ongoing) will be analyzed.

All adverse events will be listed (see Table 14).

Adverse events are classified as being general, local – TW related or local – not TW related in the eCRF. Per each of these categories, the AEs will be listed as given in Table 9 and Table 10. The listing will be presented separately by:

- System organ class
- Preferred term
- Severity (mild / moderate / severe AEs)
- Relatedness (not related / remotely related / possibly related / probably related / related AEs)
- Time of onset (until 3 months follow up [i.e. AEs from first stage that are still ongoing] / between 3 months follow up and 12 months follow up)

SAEs will be analyzed in the same way as AEs.

11.2.4.5. *Concomitant medication*

In this analysis, only the concomitant medications given after the 3 months follow up and until the 12 months follow up (including CM with a start date before the 3 months follow up but an end date after that or still ongoing at 12 months) will be analyzed.

The number of concomitant medication and patients involved will be tabulated with reference to ATC coding (see Table 12).

11.2.4.6. *Lower Extremity Function Scale (LEFS)*

The LEFS scores of the 12 months follow up assessment will be analyzed descriptively with number of units, number of missing values, mean, standard deviation, min, max, median and quartiles as presented in Table 4. The mean LEFS scores between treatment groups will be compared by a one-way analysis of variance. Histograms will be provided to illustrate the distribution of LEFS values.

11.2.4.7. *Disabilities of the Arm, Shoulder and Hand (QuickDASH)*

The QuickDASH scores of the 12 months follow up assessment will be analyzed descriptively with number of units, number of missing values, mean, standard deviation, min, max, median and quartiles as presented in Table 4. The mean QuickDASH scores between treatment groups will be compared by a one-way analysis of variance. Histograms will be provided to illustrate the distribution of QuickDASH values.

11.2.4.8. *Range of Motion (ROM)*

The 12 months range of motion will be evaluated using 3 binary (yes/no) variables. The variables indicate whether all ROM were normal, whether there was at least one abnormal (NCS) finding and whether there was at least one abnormal (CS) finding. This information is present per patient and per visit. Rates of patients with this event will be analyzed by displaying counts and percentages by treatment group (see Table 5) per variable (all normal / at least one abnormal (NCS) / at least one normal (CS)) and per visit. Furthermore, bar plots will be displayed. The proportion of patients with all normal / at least one abnormal (NCS) / at least one normal (CS) range of motion will be compared between treatment groups using a chi square test (or Fisher's exact test in case of small estimated cell counts).

11.2.4.9. *EQ-5D (Quality of Life)*

The 12 months follow up assessment of the EQ-5D will be analyzed as follows.

The EQ-5D consists of 5 items with 3 possible answers each and an EQ visual analogue scale. For each item (Mobility, Self-Care, Usual Activities, Pain/Discomfort, Anxiety/Depression) the

count and percentages of each possible answer will be presented per age group and per treatment group as in Tables 3 and 4 of the EQ-5D-3L user guide [32]. Furthermore, bar plots will be provided. The difference between treatment groups will be tested using a chi square test (or Fishers' exact test in case of small expected cell counts).

The values of the EQ visual analogue scale (EQ VAS) will be analyzed descriptively with number of units, number of missing values, mean, standard deviation, min, max, median and quartiles as presented in Table 3 of the EQ-5D-3L user guide [32]. The mean EQ VAS values between treatment groups will be compared by a one-way analysis of variance. Histograms will be provided to illustrate the distribution of EQ VAS values.

11.2.4.10. *Burn Specific Health Scale – Brief (BSHS-B)*

The 12 months follow up assessment of the BSHS-B will be analyzed as follows.

Each domain specific sub score and the overall BSHS-B score will be analyzed descriptively with number of units, number of missing values, mean, standard deviation, min, max, median and quartiles as presented in Table 4. The mean (sub-) score values between treatment groups will be compared by a one-way analysis of variance. Histograms will be provided to illustrate the distribution of (sub-) score values.

11.2.5. *Exploratory Analyses*

11.2.5.1. *POSAS*

The POSAS for target wounds will be calculated as outlined in Section 10.3.5.7 and will be analyzed descriptively with number of units, number of missing values, mean, standard deviation, min, max, median and quartiles as presented in Table 4. The mean POSAS values between treatment groups will be compared by a one-way analysis of variance. Histograms will be provided to illustrate the distribution of POSAS in the treatment groups.

The analysis will be repeated for the patient scale and for the observer scale separately.

The analysis will be repeated for donor site scars.

The analyses will be conducted for the POSAS assessments of 1, 3, 6 and 12 months.

11.2.5.2. *MVSS (target wounds)*

The MVSS for target wounds at 1, 3, and 6 months will be calculated as outlined in Section 10.3.4.2 and will be analyzed descriptively with number of units, number of missing values, mean, standard deviation, min, max, median and quartiles as presented in Table 4. The mean

MVSS values between treatment groups will be compared by a one-way analysis of variance. Histograms will be provided to illustrate the distribution of MVSS in the treatment groups.

11.2.5.3. *MVSS (donor site scars)*

The MVSS for donor site scars at 1, 3, 6 and 12 months will be calculated as outlined in Section 10.3.4.2 and will be analyzed descriptively with number of units, number of missing values, mean, standard deviation, min, max, median and quartiles as presented in Table 4. The mean MVSS values between treatment groups will be compared by a one-way analysis of variance. Histograms will be provided to illustrate the distribution of MVSS in the treatment groups.

11.2.6. **Pharmacokinetic Variables**

Not applicable. All pharmacokinetic data was already analyzed in the first stage analysis (see Section 11.1.6).

11.2.7. **Multicenter Data**

See Section 11.1.7.

11.2.8. **Handling of Multiple Comparisons**

Not applicable. All testing done during this second stage analysis is exploratory in nature. So no adjustment for multiplicity is needed.

11.2.9. **Interim analysis**

No interim analyses will be performed.

11.2.10. **Stratification**

See Section 11.1.10.

11.2.11. **Analysis of Subgroups**

11.2.11.1. *Total TBSA \leq 15%*

A subgroup analysis will be done for the patients with Total TBSA \leq 15%.

The 12 months MVSS will be analyzed descriptively with number of units, number of missing values, mean, standard deviation, min, max, median and quartiles as presented in Table 4.

The mean MVSS values between treatment groups will be compared by a one-way analysis of variance. Histograms will be provided to illustrate the distribution of MVSS in the treatment groups.

11.2.11.2. *Total TBSA > 15%*

The same analysis as in Section 11.2.11.1 will be done but on the subgroup of patients with total TBSA > 15%.

11.2.11.3. *All target wounds full thickness*

The same analysis as in Section 11.2.11.1 will be done but on the subgroup of patients with all target wounds classified as full thickness wounds.

11.2.11.4. *Mixed target wounds – full thickness and deep partial thickness*

The same analysis as in Section 11.2.11.1 will be done but on the subgroup of patients with mixed thickness target wounds (full thickness and deep partial thickness).

11.2.11.5. *All target wounds are deep partial thickness*

The same analysis as in Section 11.2.11.1 will be done but on the subgroup of patients with all target wounds classified as deep partial thickness wounds.

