10.1.2.2. Safety Endpoint: Cosmesis and function at 12 months from wound closure

A higher ratio of missing values is expected in the case of later MVSS values, especially for 24 months. It is expected that the 1 months MVSS value exists. If this is not the case the missing MVSS value will be replaced by the mean MVSS value of all patients who belong to the same treatment group and the same stratum (see Section 11.1.10) at that time point. For missing MVSS values at later time points (3, 6, 12, 18 and 24 months) the following imputation method will be used:

For each time point (1, 3, 6 and 12 months) and each treatment arm separately, a linear regression model with target variable MVSS at 12 months and explanatory variables MVSS at the respective time point and all stratification variables (see Section 11.1.10) is fitted to the data of patients having both MVSS values. Missing MVSS values at 12 months are then

imputed with the prediction of the linear regression model, which has the last non-missing MVSS value before the 12 months measurement for the individual as explanatory variable (i.e. for patients who have the 6 months MVSS measurement but not the 12 months measurement, the 12 months measurement is imputed from the 6 months measurements; for those who have the 3 months measurement but not the 6 months or 12 months measurement the 12 months measurement is imputed from the 3 months measurement; and for those who have the MVSS measurement at 1 month but not at 3 months, 6 months or 12 months the 12 months measurement will be imputed from the 1 month measurement). To this prediction, the realization of a normally distributed random variable with zero mean and standard deviation equal to the residual standard deviation from the linear model is added. The random seed for this imputation is 45318.

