11.1.10. Stratification

The following factors are used to stratify the study design:

A. Total TBSA % per patient

A1: Total TBSA <=15%

A2: Total TBSA >15%

B. Overall depth per patient

B1: All TWs are full thickness;

B2: Mixed TWs – full thickness and deep partial thickness

B3: All TWs are deep partial thickness.

C. Center Group, to address possible differences in SOC procedures between sites (if any), to allow comparison of the results within group of centers and to reduce the likelihood of a group of centers including patients in only one arm of the study (5 groups of centers were formed based on similarity of SOC practice).

These factors are accounted for in the analyses of the primary and secondary endpoints by including them as adjusting variables.

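### The 12- and 24-month MVSS models are described as adjusted for the stratification factors, but they omit centre group, one of the three.

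*SAP*

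**What the plan says.** SAP 11.2.4.2 sets out a linear model for the patient's MVSS score at 12 months: "The explanatory variables in the model will include treatment, and the following variables: overall TW depth", followed by total %TBSA per patient and number of target wounds in three classes. The list ends there. The treatment coefficient is then described as "adjusted for any imbalance in the stratification factors", and the same description is attached to the Δ of the hypotheses. The test is made by "comparing the 95% confidence interval for the coefficient of the treatment group from the linear model outlined above" with 1.9: "The null hypothesis will be rejected if the upper bound of this interval is smaller than 1.9". SAP 11.3.4.3 repeats the covariates, the description and the rule at 24 months.

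SAP 11.1.10 lists total TBSA (two levels), overall depth (three levels) and "C. Center Group, to address possible differences in SOC procedures between sites", the last with five levels.

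SAP 10.1.2.2 imputes missing 12- and 24-month MVSS values from regressions fitted separately by arm. Their predictors are "MVSS at the respective time point and all stratification variables (see Section 11.1.10". Centre group is therefore in the imputation models. Number of target wounds is not.

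**The concern.** The tested quantity is defined with one adjustment set and estimated with another. A reader of the results would take the difference to be adjusted for all three factors. SAP 6.4 has the MVSS assessments programmed a second time by an independent statistician, and two programmers could reasonably fit different models from this text.

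There is also a statistical cost to consider. Stratified randomisation balances the arms within centre groups, so the treatment estimate already benefits from that balance. A model without centre group leaves any centre variation in the residual and reports a standard error that ignores the benefit. If centre group is prognostic, the upper bound compared with 1.9 is then higher than it need be. Study objective 3 (SAP 2.2) includes long-term cosmesis and function, and these are the SAP's margin tests for them.

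**Working it through.** **Text check.** The factors in 11.1.10, set against the two MVSS models:

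| Factor | 11.2.4.2 and 11.3.4.3 | Imputation, 10.1.2.2 |
|---|---|---|
| Total TBSA | in | in |
| Overall depth | in | in |
| Centre group | **absent** | in |
| Number of target wounds (not a stratification factor) | in | **absent** |

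Sections 11.2.7, 11.2.10, 11.3.7 and 11.3.10 only point back to 11.1.7 and 11.1.10. Those promise adjustment for the primary and secondary endpoints. MVSS is a safety endpoint, so the cross-references do not fill the gap.

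**Size.** The SAP gives no MVSS power, standard deviation or interval width, so there is no figure of its own to reproduce.

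Inputs from the SAP: 75 patients per arm (9.3.1), margin 1.9, two-sided 95% interval, five centre groups.

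Assumed inputs: R², the share of residual MVSS variance explained by centre group, from 0 to 0.30; and a residual SD of 2.25 to 4.5. The SD range is a quarter to a half of the 0 to 9 range observed in the earlier study's SOC arm (10.1.2.2).

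Half-width = t(0.975, df) × SD × √(1 − R²) × √(2/75).

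- Centre omitted: R² term set to 0, df = 150 − 7 = 143.
- Centre included: df = 150 − 11 = 139.

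For SD 3:

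| R² | Half-width, omitted | Half-width, included | Ratio |
|---|---|---|---|
| 0 | 0.968 | 0.969 | 1.00 |
| 0.05 | 0.968 | 0.944 | 1.03 |
| 0.10 | 0.968 | 0.919 | 1.05 |
| 0.20 | 0.968 | 0.866 | 1.12 |
| 0.30 | 0.968 | 0.810 | 1.20 |

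The ratio does not depend on the SD. Power against 1.9 at a true difference of 0 (noncentral t) does:

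| SD | Omitted | Included, R² 0.10 | Included, R² 0.20 |
|---|---|---|---|
| 2.25 | 0.999 | 1.000 | 1.000 |
| 3 | 0.971 | 0.982 | 0.991 |
| 4 | 0.824 | 0.861 | 0.898 |
| 4.5 | 0.728 | 0.772 | 0.819 |

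**Direction of the error.** A simulation used 175 patients, 3:3:1 permuted blocks of seven within depth × TBSA × centre group, and SD 3. Block design, stratum frequencies and SD are assumed. There were 4,000 runs at a true difference of 1.9 and 1,500 at 0.6.

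| R² | SD of estimate, omitted | Mean model SE, omitted | One-sided error at 1.9, omitted / included | Power at true difference 0.6, omitted / included |
|---|---|---|---|---|
| 0 | 0.500 | 0.494 | 0.0245 / 0.0250 | 0.74 / 0.74 |
| 0.10 | 0.474 | 0.495 | 0.0210 / 0.0235 | 0.73 / 0.77 |
| 0.20 | 0.459 | 0.494 | 0.0173 / 0.0260 | 0.75 / 0.83 |
| 0.30 | 0.435 | 0.495 | 0.0132 / 0.0238 | 0.77 / 0.88 |

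The estimate is unbiased in both models. Without centre group the reported standard error stays near 0.495 while the true variability falls, so the error at the margin drops below the nominal 0.025.

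**The case against.** The omission may be deliberate. The version 9 amendment log records trimming the analyses to the most influential terms. The main model for surgical excision uses the same covariates as the MVSS model, with centre only in a supportive analysis. That explains why a short list might be chosen, but not why its coefficient is then called adjusted for the stratification factors. The reservation about numerical feasibility in the logistic model has little force in a linear model with about 150 patients. Safety status alone does not explain the omission either, since the fallback model for time to wound closure (11.1.4.1) carries centre-group indicators.

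It is fair that deleting the adjustment statement would also remove the contradiction. It would not recover any lost precision. It is also fair that second- and third-stage tests are labelled exploratory (11.2.8, 11.3.8), which limits the consequence.

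A reader might infer more than the SAP supports:

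- *That the interval is in fact too wide.* This needs a centre effect. The SAP states none and treats differences in SOC between sites as only possible. The single random imputation in 10.1.2.2, analysed as observed data, tends to narrow the interval, so the net width is not settled.
- *That non-inferiority is harder to show than the design allows.* The sample size rests on the primary and two secondary endpoints, and MVSS has no power target.
- *That differences between assessors stay in the error for want of this term.* Centre groups were formed on SOC practice and assessors are appointed per site, so a five-level factor would not generally remove assessor differences.
- *That centre group in the imputation but not the analysis is a serious mismatch.* A richer imputation model is the milder direction. The reverse gap, number of target wounds, deserves more attention.

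**Conclusion.** The concern stands as an inconsistency in the text with a possible, conservative cost. Both MVSS models claim adjustment for the stratification factors and leave out one of three. That finding rests on the SAP's wording alone.

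The cost rests on assumptions. The model-based interval is wider than it need be by nothing at R² = 0, about 3% at 0.05, 5% at 0.10 and 12% at 0.20. Against 1.9 at 75 per arm, with no true difference, this hardly matters at an SD of 3 or below. It becomes noticeable if the SD is near 4 or more, if centre group explains a larger share, or if the true difference is well above zero. With fewer evaluable patients power is lower throughout, but the ratio of widths barely changes: at 50 per arm it is still 1.05 for R² = 0.10.

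It would be wrong to conclude that the omission could give false reassurance on scarring. In the simulation the error rate at the margin falls when centre group is left out. The effect of omitting number of target wounds from the imputation cannot be sized from the SAP.

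**What to change.** In SAP 11.2.4.2 and 11.3.4.3, add centre group (five levels, as in 11.1.10) as a fixed factor in the linear model, so that the adjustment statement becomes true. In 10.1.2.2, add number of target wounds (1, 2, ≥3) to the predictors of the 12- and 24-month imputation models, so that every analysis covariate is also in the imputation.

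The cost is one phrase in each of the two analysis sections and a short addition in the imputation section. In the analysis it takes 4 degrees of freedom, from 143 to 139 at full enrolment. If centre group does not predict MVSS, the half-width at SD 3 moves only from 0.968 to 0.969. The imputation regressions gain two parameters each. The change should be fixed before MVSS data are analysed by arm.

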11.3. Third stage analysis – 24 month long-term safety follow-up (LTSFU24)

11.3.1. Demographics and Other Baseline Characteristics

Not applicable for this stage of analysis since all information on demographics and other baseline characteristics was already analyzed in the first stage analysis (see 11.1.1).

11.3.2. Primary Efficacy variable

Not applicable for this stage of analysis since all information on the primary efficacy variable was already analyzed in the first stage analysis (see 11.1.2).

11.3.3. Secondary Efficacy variables

Not applicable for this stage of analysis since all information on the secondary efficacy variables was already analyzed in the first stage analysis (see 11.1.3).

11.3.4. Safety variables

11.3.4.1. Safety Endpoint: Time to wound closure

Not applicable for this stage of analysis since all information on this endpoint was already analyzed in the first stage analysis (see 11.1.4.1).

11.3.4.2. Safety Endpoint: Cosmesis and function at 12 months from wound closure

Not applicable for this stage of analysis since all information on this endpoint was already analyzed in the second stage analysis (see 11.2.4.2).

11.3.4.3. Safety Endpoint: Cosmesis and function at 24 months from wound closure

The MVSS score for a patient will be calculated as described in Section 10.3.4.3. The mean and standard error of this MVSS score (for the target wounds) at 24 months will be estimated for each treatment group and presented as shown in Table 4. The treatment groups will be compared using a linear model with MVSS score as the dependent variable. The explanatory variables in the model will include treatment, and the following variables: overall TW depth (all TWs full thickness, mixed TWs, all TWs deep partial thickness), "Total

%TBSA per patient" and number of TWs (1, 2, ≥ 3). The coefficient corresponding to the treatment group will be estimated and will represent the estimated mean difference in MVSS score between NexoBrid and SOC adjusted for any imbalance in the stratification factors. The results of the regression analysis will be presented as in Table 7.

A clinically meaningful difference will be incorporated into the analysis that will represent a 1.9 or more units advantage to the SOC group, so that the analysis will show whether the NexoBrid group is estimated to have on average a MVSS score that is not worse by more than 1.9 units than the score for the SOC group. That is, the following hypothesis are about to be tested:

$$H_0: \Delta \geq 1.9 \quad vs. \quad H_1: \Delta < 1.9$$

Where Δ is the mean difference in MVSS score between NexoBrid and SOC adjusted for any imbalance in the stratification factors. These hypotheses will be tested by comparing the 95% confidence interval for the coefficient of the treatment group from the linear model outlined above to the clinically meaningful difference 1.9. The null hypothesis will be rejected if the upper bound of this interval is smaller than 1.9.

For handling of missing data, see Section 10.1.2.2.

